7.1.1.1 Reporting a Pause

If a pausing criterion is met, then a description of the AE(s) or safety issue must be reported to the NIH IRB per NIH Human Research Protection Program (HRPP) Policy 801.

7.1.1.2 Resumption of Study Agent After a Pause

The principal investigator will determine whether it is safe to resume administration of the study agent to the participant, and will notify the IRB of the decision on resumption of the study agent.

7.1.1.3 Discontinuation of Study Agent

A participant who does not resume study agent will continue to be followed for safety.

7.1.2 Halting Rules for the Protocol

Halting the study requires immediate discontinuation of study agent administered for all participants and suspension of enrollment until a decision is made whether to continue enrollment and study agent administration.

The halting rules are:

- Two or more participants experience the same or similar grade 3 or higher AEs that are unexpected and possibly, probably, or definitely related to the study agent or study procedures.
- Two or more participants experience the same or similar SAEs that are unexpected and possibly, probably, or definitely related to the study agent or study procedures.
- Any safety issue the investigators determine should halt the study.

The principal investigator will determine if the study should be halted. The IRB may halt the study at any time.

7.1.2.1 Reporting a Study Halt

If a halting rule is met, then a description of the AE(s) or safety issue must be reported to the IRB according to their requirements.

7.1.2.2 Resumption of a Halted Study

The principal investigator will determine if it is safe to resume the study, and will notify the IRB of the decision on resumption of the study.

7.1.2.3 Discontinuation of Study Agent

Participants who do not resume study agent will continue to be followed for safety.

7.2 PARTICIPANT DISCONTINUATION/WITHDRAWAL FROM THE STUDY

An individual participant will be withdrawn from the study for any of the following:

- An individual participant's decision. (The investigator should attempt to determine the reason for the participant's decision.)
- Non-compliance with study procedures to the extent that it is potentially harmful to the participant or to the integrity of the study data. For example, the participant does not complete the full BSS regimen.
- Participant is unable to provide ongoing informed consent.
- The participant becomes pregnant before day 0.
- The investigator determines that continued participation in the study would not be in the best interest of the participant.

Participants who withdraw or are withdrawn from the study prior to day 14 will be replaced. If a participant is replaced, then all the data collected from that participant will still be included for the safety assessment.

7.3 LOST TO FOLLOW-UP

A participant will be considered lost to follow-up if they fail to return for 3 scheduled visits and is unable to be contacted by the study site staff.

The following actions must be taken if a participant fails to return to the clinic for a required study visit:

- The site will attempt to contact the participant and reschedule the missed visit within the timeframe allowable by the study windows and counsel the participant on the importance of maintaining the assigned visit schedule and ascertain if the participant wishes to and/or should continue in the study.
- Before a participant is deemed lost to follow-up, the investigator or designee will make every effort to regain contact with the participant (where possible, 3 telephone calls and, if necessary, a certified letter to the participant's last known mailing address or local equivalent methods). These contact attempts should be documented in the participant's medical record or study file.
- Should the participant continue to be unreachable, they will be considered to have withdrawn from the study with a primary reason of lost to follow-up.

8 STUDY ASSESSMENTS AND PROCEDURES

8.1 SCREENING PROCEDURES

The following minimal risk activities may be performed before the participant has signed the informed consent form:

- Email, written, in-person or telephone communications with prospective participants.
- Review of existing medical records, including but not limited to history and physical examination, laboratory studies, imaging (eg, X-ray or computed tomography), and diagnostic pathology specimens and reports.

8.2 STUDY EVALUATIONS & PROCEDURES

Targeted physical exam: The components of the exam will be at the discretion of the investigator. Weight and vital signs will be measured.

Baseline questionnaire: This will include questions regarding demographics, medical history, and medications. Participants may complete this questionnaire on paper or electronically via REDCap system.

Survey: A brief survey containing questions regarding diet and other factors that can affect the gut microbiome will be administered at each visit. Participants may complete this questionnaire on paper or electronically via REDCap.

Colonoscopy: Colonoscopy is an optional procedure for collection of intestinal biopsies and brushings. This procedure will be limited to those 30 years of age or younger. This is because the chance of incidental findings such as intestinal polyps are lower at this age.⁽³⁹⁾ If an incidental polyp was found, a polypectomy may need to be carried out at the discretion of the gastroenterologist performing the procedure, and this increases the risk of a colonoscopy.

Up to 20 research biopsies may be obtained from the colon and ileum. If a participant agrees to this procedure, then they will undergo it at baseline and the day 8 visit. Baseline has a window between weeks -18 and -1, so it will be scheduled relative to day 0 so there are at least 30 days between colonoscopy procedures. Colonoscopy preparation will be per standard process, and participants will be instructed accordingly. Before the first procedure to ensure participant safety,

participants will have a GI consultation, a pre-anesthesia consultation, clinical blood evaluations (section 8.2.1), and a pregnancy test (if of childbearing potential); an ECG and chest X-ray may be conducted if they are determined to be needed per the Department of Perioperative Medicine guidelines at the NIH CC. These procedures, except the pregnancy test, will only be repeated up to 8 days before the second procedure if there are more than 30 days between colonoscopies and if they are determined to be needed per the Department of Perioperative Medicine guidelines at the NIH CC. A pregnancy test will always be done before both colonoscopies for participants who can get pregnant. Biopsies and brushings will be collected for research purposes, as described in section 8.2.1.

8.2.1 Biospecimen Evaluations

Stool: Stool is the only required sample and will be collected at all study visits. For remote visits, participants will be provided with an at-home collection kit, which they can ship to the NIH. Participants may not be able to provide a stool sample at all visits. The minimum number of samples required for this study (ie, that does not constitute a protocol deviation, section 10.9) is 1 sample before starting the BSS regimen and 1 sample after completion of the regimen. Research evaluations on stool samples will include the following:

- Microbiome sequencing (including 16S ribosomal [r]RNA gene sequencing, shotgun metagenomic sequencing and evaluation of the resistome, virome, and parasitome).
- Metabolomics to evaluate intestinal metabolomic profiles, and when combined with microbiome/metagenomic studies, may suggest some functional role for candidate microbes of interest.
- Fecal flow (sorting and 16S and/or shotgun sequencing of immunoglobulin [Ig]A-bound organisms, which is an indication of pathogenicity).
- Lipocalin, calprotectin, and α -1-anti-trypsin levels (to evaluate mucosal inflammation and malabsorption).
- Measurement of secreted IgA and antimicrobial peptides.
- Culturing/polymerase chain reaction for specific organisms.
- Stool proteomics.
- Use of stool samples in murine models.
- Metatranscriptomics (the gene expression of the microbiota and host).
- Storage for future research.

Blood: Blood is an optional sample that will only be collected at in-person visits. Between 30 to 150 mL of blood will be collected per visit. The amount of blood drawn for research purposes will be within the limits allowed for adult research participants by the NIH CC (Medical Administrative Policy 95-9, Guidelines for Limits of Blood Drawn for Research Purposes in the Clinical Center: <http://cc-internal.cc.nih.gov/policies/PDF/M95-9.pdf>). Research evaluations on blood include the following:

- Host immune and inflammatory responses, and specific responses to the microbiome.
- Metabolomics.
- Lipopolysaccharide and lipopolysaccharide-binding protein (for evaluation of bacterial translocation and intestinal permeability).

Abbreviated Title: BSS Gut Microbiome

Version Date: 05 July 2024

- Isolation and cryopreservation of peripheral blood mononuclear cells and serum (for the creation of induced pluripotent stem [iPS] cells and future evaluation of systemic immune responses).
- Blood for RNA sequencing (seq) for evaluation of bacterial translocation and intestinal permeability, and host gene expression.
- Storage for future research.

Blood will be used for the following clinical evaluations only in those undergoing colonoscopy:

- Complete blood count with differential.
- Acute care, hepatic, and mineral panels.
- Coagulation studies: prothrombin time, partial thromboplastin time, international normalized ratio, PFA.

Urine: Urine is an optional sample. For remote visits, participants will be provided with an at-home collection kit, which they can ship to the NIH. Research evaluations on urine include the following:

- Metabolomics and trimethylamine N-oxide measurements.
- Microbiome sequencing (including 16S rRNA gene sequencing, shotgun metagenomic sequencing and evaluation of the resistome, virome, and parasitome).
- Immune and inflammatory responses (eg, using SomaLogic's SOMAscan assay).
- Oxalate level.
- Urinalysis.
- Storage for future research.

Saliva: Saliva is an optional sample. For remote visits, participants will be provided with an at-home collection kit, which they can ship to the NIH. Research evaluations on saliva include the following:

- Microbiome sequencing (including 16S rRNA gene sequencing, shotgun metagenomic sequencing and evaluation of the resistome, virome, and parasitome).
- Host immune and inflammatory responses.
- Metabolomics.
- Storage for future research.

Intestinal biopsies and brushings: As described in section 8.2, participants have the option to provide intestinal biopsies and brushings for the following research evaluations:

- Microbiome sequencing (including 16S rRNA gene sequencing, shotgun metagenomic sequencing and evaluation of the resistome, virome, and parasitome).
- Immunophenotyping.
- Immunohistochemistry and fluorescence in situ hybridization
- Generation of cell suspensions and sorting of cells for functional studies.
- Cell type-specific transcriptome and metabolomics analysis.
- Gene expression analysis (RNA-seq).
- Generation of iPS cells and organoids.
- Tissue fixing and stains for microscopy (eg, hematoxylin and eosin stain).
- Storage for future research.

8.2.2 Samples for Genetic/Genomic Analysis

8.2.2.1 Description of the Scope of Genetic/Genomic Analysis

Blood, stool, urine, and intestinal biopsy and brushing samples will be used for gene expression analysis (eg, RNA-seq and transcriptomics) and microbiome sequencing (eg, 16S rRNA gene sequencing and shotgun metagenomic sequencing, and potential evaluation of the resistome, virome, and parasitome).

These genetic analyses are for research purposes only and will not be validated in a laboratory certified under the Clinical Laboratory Improvement Amendments.

8.2.2.2 Description of How Privacy and Confidentiality of Medical Information/Biological Specimens Will Be Maximized

Confidentiality and privacy protections on this study, which includes genetic data, are described in section [10.3](#).

8.2.2.3 Management of Primary Results

Human sequences present in microbiome datasets will not be evaluated and will be removed prior to sharing in a repository. Therefore, there will be no genetic results to return to the participant.

8.2.2.4 Return of Secondary Genomic Research Results

Not applicable.

8.3 SAFETY AND OTHER ASSESSMENTS

Information collected from clinical and biospecimen evaluations (section [8.2](#)) will be reviewed for ongoing safety assessments.

Any clinically relevant test results will be shared with the participant throughout the study. Results of research procedures or evaluations (including incidental findings) will be shared with participants if they are medically actionable. Such results will be discussed with the participant along with guidance for appropriate follow-up with their healthcare provider. Any research findings discovered beyond the completion of the primary research will not be returned.

Colonoscopic examination may lead to incidental discovery of lesions that require further study to rule out malignancy. Because this study is not designed for purposes of diagnosis or screening, the decision to perform follow-up examination or obtain biopsies of such lesions will be under the discretion of the principal investigator or the endoscopist. Biopsy-proven malignant or potentially malignant lesions will be immediately reported and discussed with the participant, and assistance for appropriate referral will be provided in a timely fashion. In addition, pathologic slides will be made available to an outside pathologist for review if requested in the future. Any suspicious-looking lesion where no biopsy is done will likewise be discussed with the participant for appropriate follow-up with the participant's healthcare provider.

8.4 ADVERSE EVENTS AND SERIOUS ADVERSE EVENTS

8.4.1 Definition of Adverse Event

AEs are any untoward medical occurrence associated with the use of an intervention in humans, whether or not considered intervention-related (21 CFR 312.32 (a)).

8.4.2 Definition of Serious Adverse Events

An AE or suspected adverse reaction is considered “serious” if, in the view of the investigator, it results in any of the following outcomes: death, a life-threatening AE, inpatient hospitalization or prolongation of existing hospitalization, a persistent or significant incapacity or substantial disruption of the ability to conduct normal life functions, or a congenital anomaly/birth defect. Important medical events that may not result in death, be life-threatening, or require hospitalization may be considered serious when, based upon appropriate medical judgment, they may jeopardize the participant and may require medical or surgical intervention to prevent one of the outcomes listed in this definition. Examples of such medical events include allergic bronchospasm requiring intensive treatment in an emergency room or at home, blood dyscrasias or convulsions that do not result in inpatient hospitalization, or the development of drug dependency or drug abuse.

8.4.3 Definition of Adverse Event of Special Interest

Adverse events of special interest (AESIs) are AEs that will be handled in a protocol/study-specific manner that differs from statutory and general rules for reporting. For the purposes of this protocol, AESIs are limited to any grade 2+ AEs probably or definitely related to gastrointestinal research biopsy collection.

8.4.4 Classification of an Adverse Event

8.4.4.1 Severity of Event

The investigator will grade the severity of each AE according to the Division of AIDS Table for Grading the Severity of Adult and Pediatric Adverse Events” Version 2.1, July 2017 which can be found at <https://rsc.niaid.nih.gov/sites/default/files/daidsgradingcorrectedv21.pdf>. Instructions provided in this toxicity table for estimating the severity grade for parameters not specifically identified in the table will be used for grading those events.

8.4.4.2 Relationship to Study Intervention

All AEs must have their relationship to study intervention assessed by the investigator who examines and evaluates the participant based on temporal relationship and their clinical judgment. The degree of certainty about causality will be graded using the categories below. In a clinical trial, the study product must always be suspect.

Definitely Related – There is clear evidence to suggest a causal relationship, and other possible contributing factors can be ruled out. The clinical event, including an abnormal laboratory test result, occurs in a plausible time relationship to study intervention administration and cannot be explained by concurrent disease or other drugs or chemicals. The response to withdrawal of the study intervention (dechallenge) should be clinically plausible. The event must be pharmacologically or phenomenologically definitive, with use of a satisfactory rechallenge procedure if necessary.

Probably Related – There is evidence to suggest a causal relationship, and the influence of other factors is unlikely. The clinical event, including an abnormal laboratory test result, occurs within a reasonable time after administration of the study intervention, is unlikely to be attributed to concurrent disease or other drugs or chemicals, and follows a clinically reasonable response on withdrawal (dechallenge). Rechallenge information is not required to fulfill this definition.

Potentially Related – There is some evidence to suggest a causal relationship (eg, the event occurred within a reasonable time after administration of the trial medication). However, other factors may have contributed to the event (eg, the participant’s clinical condition, other concomitant events). Although an AE may rate only as “possibly related” soon after discovery, it can be flagged as requiring more information and later be upgraded to “probably related” or “definitely related”, as appropriate.

Unlikely to be related – A clinical event, including an abnormal laboratory test result, whose temporal relationship to study intervention administration makes a causal relationship improbable (eg, the event did not occur within a reasonable time after administration of the study intervention) and in which other drugs or chemicals or underlying disease provides plausible explanations (eg, the participant’s clinical condition, other concomitant treatments).

Not Related – The AE is completely independent of study intervention administration, and/or evidence exists that the event is definitely related to another etiology. There must be an alternative, definitive etiology documented by the clinician.

8.4.4.3 Expectedness

The investigators will be responsible for determining whether an AE is expected or unexpected. An AE will be considered unexpected if the nature, severity, or frequency of the event is not consistent with the risk information previously described for the study drug/procedure.

8.4.5 Time Period and Frequency for Event Assessment and Follow-Up

At each contact with the participant, information regarding AEs will be elicited by appropriate questioning and examinations. All events, both expected/unexpected and related/unrelated will be recorded on a source document. Source documents will include progress notes, laboratory reports, consult notes, phone call summaries, survey tools, and data collection tools. Source documents will be reviewed in a timely manner by the research team. All reportable AEs that are identified will be recorded in CRIMSON. The start date, the stop date, the severity of each reportable event, and the principal investigator’s judgment of the AE’s relationship and expectedness to the study agent/intervention will also be recorded in CRIMSON.

AEs that have not resolved by the end of the follow-up period will be followed until final outcome is known. If it is not possible to obtain a final outcome for an AE (eg, the participant is lost to follow-up), the reason a final outcome could not be obtained will be recorded by the investigator in CRIMSON.

8.4.6 Adverse Event Reporting

AEs will be reported to the NIH IRB per NIH HRPP Policy 801.

8.4.7 Serious Adverse Event Reporting

SAEs will be reported to the NIH IRB per NIH HRPP Policy 801.

8.4.8 Adverse Events of Special Interest (Expedited Reporting)

Unless otherwise specified above, all AESIs must be reported to the NIAID Clinical Safety Office (CSO) as specified by the CSO (eg, Research Electronic Data Capture [REDCap] system; use the Safety Expedited Report Form [SERF]/email if REDCap is not available). If the preferred/indicated mechanism for reporting is not available, the CSO/medical monitor (MM)

Abbreviated Title: BSS Gut Microbiome

Version Date: 05 July 2024

should be contacted by telephone, fax, or other reasonable mechanism to avoid delays in reporting.

CSO CONTACT INFORMATION:

Clinical Safety Office

[name]

[name]

[contact]

[contact]

Email: [contact]

<https://crimsonredcap.cc.nih.gov/redcap/index.php>

Unless otherwise specified above, deaths and immediately life-threatening SAEs must be reported to the CSO/MM promptly, and no later than the **first business day** following the day of study personnel awareness.

All other SAEs must be reported to the CSO/MM no later than the **third business day** following the day of study personnel awareness.

8.4.9 Reporting of Pregnancy

Although pregnancy itself is not an AE, events occurring during pregnancy, delivery, or in the neonate (eg, congenital anomaly/birth defect) may be AEs or SAEs. We will assess pregnancy status at the baseline visit and before colonoscopy by urine pregnancy test in those who can become pregnant.

If a participant becomes pregnant before the first dose of BSS on day 0, then they will be withdrawn from the study (section 7.2). In the event of pregnancy after they start the BSS regimen, the following steps will be taken:

- Discontinue the study agent and procedures but continue to follow-up as scheduled for safety until the end of study participation to ensure no adverse effects have occurred.
- Report to the IRB.
- Advise research participant to notify the obstetrician of study participation and study agent exposure.

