
AE, adverse event; BSS, bismuth subsalicylate; CBC/diff, complete blood count with differential; ECG, electrocardiogram; GI, gastrointestinal; PT/PTT/INR, prothrombin time, partial thromboplastin time, and international normalized ratio; X, to be performed.
 
a Baseline will be done after confirmation of eligibility. The overlap between the screening and baseline windows accounts for the required 30-day interval between the optional colonoscopies at baseline and day 8. Participants who do not undergo colonoscopy may have a shorter interval between screening, baseline, and day 0.
 
b The informed consent form will be signed before any research procedures are conducted on this study.
 
c Limited review of existing medical records may be done before the participant signs the informed consent form.
 
d Continued eligibility will be confirmed at the baseline visit.
 
e For participants of childbearing potential only. If the visit will be done remotely, then the participant will be instructed to send a urine sample to the study team, which will be used for pregnancy testing.
 
f For participants who will have the baseline colonoscopy, the timing of baseline pregnancy test will be per Department of Perioperative Medicine guidelines.
 
g To avoid repetition of procedures, pregnancy test will only be done at day 0 if baseline was more than 14 days before.
 
h Pregnancy test will only be done at day 8 if the participant will undergo the colonoscopy.
 
i Day 0 stool, which will be collected before first dose of BSS, may be collected up to 7 days earlier. For participants undergoing colonoscopy, stool samples will be attempted to be collected prior to the start of the bowel preparation.
 
j These procedures will only be done if the participant is undergoing the colonoscopy and the procedures are determined to be needed per the Department of Perioperative Medicine guidelines at the NIH Clinical Center. These labs will be repeated for the second (day 8) colonoscopy per the Department of Perioperative Medicine and if there are more than 30 days between it and the first procedure. For the convenience of the participant and study team, blood for the second colonoscopy may be drawn at the day 0 or 2 visits (the latter only if in person at the NIH Clinical Center).
 
k These procedures will only be done if the participant is undergoing the colonoscopy.
 
l Research blood draw is optional and will only be offered at in-person visits.
							

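### Section 8.4.9 ends follow-up of a BSS-exposed pregnancy at the last study visit, months before the delivery and neonatal events it names could be seen

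*Combined protocol and SAP*

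**What the plan says.** Section 8.4.9 (Reporting of Pregnancy) states that pregnancy is not itself an adverse event, but that "events occurring during pregnancy, delivery, or in the neonate (eg, congenital anomaly/birth defect) may be AEs or SAEs". It then gives two branches.

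- **Before dosing.** "If a participant becomes pregnant before the first dose of BSS on day 0, then they will be withdrawn from the study". The matching withdrawal criterion is in 7.2: "The participant becomes pregnant before day 0".
- **After the regimen starts.** Dosing and study activities stop. Staff are then to "continue to follow-up as scheduled for safety until the end of study participation to ensure no adverse effects have occurred". The IRB must also be informed, and the last step reads: "Advise research participant to notify the obstetrician of study participation and study agent exposure".

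The Schedule of Activities (1.3) puts the last visit at day 28 ± 7. On testing, its footnote g says that the "pregnancy test will only be done at day 0 if baseline was more than 14 days before", and footnote h says: "Pregnancy test will only be done at day 8 if the participant will undergo the colonoscopy". Section 5.1 requires contraception from consent to the final visit. Section 5.3.1 excludes pregnant people because BSS is not recommended in pregnancy.

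**The concern.** The section names delivery and neonatal events, with congenital anomaly as the example, and gives follow-up the purpose of showing that no harm occurred. It then stops follow-up about a month after dosing. For an exposed pregnancy, the outcomes it names fall well after that point, and the study would learn of them only if someone volunteered the information.

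What is at stake is safety ascertainment in a rare situation. The primary, secondary and exploratory analyses are untouched.

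**Working it through.** **Inputs.** Last visit day 28 ± 7 (1.3). Eight doses over 2 days from day 0, with day 2 described as the day after therapy (6.1.2, 9.1), so dosing days are 0 and 1. Baseline about 1 to 18 weeks before day 0 (4.1). Day 0 test only if baseline was more than 14 days earlier (1.3, footnote g). Second colonoscopy at day 8 ± 3, at least 30 days after the first (1.3, 8.2). Assumed, not in the documents: delivery 245 to 280 days after conception; urine-test lag 0 to 14 days; no exposure after the last dose.

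**1. The plan's own figure.** Participant duration = 18 + 28/7 = 22 weeks, which matches the synopsis. With the ± 7-day window it is 21 to 23 weeks.

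**2. End of participation.** 28 − 7 = day 21; 28 + 7 = day 35.

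**3. Conception days with possible exposure, ignoring test lag.**
- Day 0 test done: conception on day 0 or 1, so 2 days.
- No day 0 test (baseline about 7 to 14 days before): 7 + 2 = 9 to 14 + 2 = 16 days.
- Colonoscopy participants: the second procedure falls on day 5 to 11, so the first is no later than day 5 − 30 = −25 to 11 − 30 = −19. Since 19 > 14, a day 0 test is due and the 2-day figure applies. The 9 to 16 day span therefore mainly concerns participants without colonoscopy.
- With a test lag of 0 to 14 days: 2 to 16 days with the day 0 test, and 9 to 30 days without it.

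**4. Days past conception at the last visit.** Minimum 21 − 1 = 20. Maximum 35 + 14 = 49, or 49 + 14 = 63 with the lag.

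**5. Days left to delivery.** Shortest 245 − 49 = 196, or 245 − 63 = 182 with the lag. Longest 280 − 20 = 260.

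**6. Where the clause is adequate.** Conception on days 0 to 35 covers 36 days. Of these, 2 overlap dosing and 34 do not; for the 34, ending at the last visit is reasonable. If exposure is assumed to last w days beyond the last dose, the split becomes 2 + w and 34 − w.

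**7. Other provisions that could reach the outcome.**
- 8.4.5 follows adverse events still open at the end of follow-up to their final outcome. A pregnancy uneventful at last contact is not an open event.
- 8.4.2 counts a congenital anomaly as serious, and 8.4.8 requires serious events to be reported once staff know of them. No step after the last visit makes staff aware.
- 7.1.1.3 and 7.1.2.3 keep participants who do not resume the agent under safety follow-up with no end date. They apply to pauses and halts and do not mention pregnancy outcome.
- 8.5 covers unanticipated problems, including harm to others, but also depends on someone knowing.
- 9.3.1 makes dosed participants evaluable for toxicity without setting a length of follow-up.

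None of these orders collection of the outcome.

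**The case against.** The case for leaving the text alone is fair. BSS is a marketed over-the-counter product given at label dose for 2 days and is IND-exempt (6.1.1, 6.1.2). Contraception is required, pregnancy is tested for, and n=20. The IRB is told of a post-start pregnancy and can ask for more; the obstetrician is to be told of the exposure; a known congenital anomaly is reportable with no stated cut-off. No rule in the documents is breached. The safety review and communications plan (10.5.1), HRPP Policy 801 and the consent form are not visible and may already provide outcome follow-up.

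All of this narrows the gap, and it is why the point ranks low. It does not close it in the protocol text, because every listed safeguard reacts to information that nobody is asked to obtain.

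A reader might also infer something stronger: that a participant who conceived before day 0, was missed because the day 0 test was skipped, and took all 8 doses would fall in the pre-dose branch and be withdrawn with no follow-up, IRB report or obstetrician advice. The documents do not support that as a demonstrated gap. The post-start steps begin with stopping the agent, and dosing lasts only days 0 and 1, so a pregnancy recognised in time to stop it would in practice have been conceived before day 0. The advice about exposure likewise presupposes an exposed pregnancy. The steps make most sense if pregnancies are sorted by when they become known, and on that reading this participant receives the post-start steps. What remains is wording that could be read two ways.

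**Conclusion.** The point holds as a cheap improvement of low importance. For an exposed pregnancy, the follow-up stated in 8.4.9 ends about 20 to 49 days after conception and at least 182 days before delivery under the declared assumptions. It cannot deliver its stated purpose for delivery and neonatal outcomes. For conceptions clearly after dosing the clause is adequate. Few or no cases are expected, and no analysis result changes.

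The conclusion is limited to the protocol text; it does not show that the study as run lacks outcome follow-up. The count of exposed conception days assumes no exposure after the last dose, and the documents give no elimination data to test that. The main conclusion does not depend on that count: on any assumption in the ranges above, the last visit falls months before delivery.

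**What to change.** In 8.4.9, for any participant who took at least one BSS dose and whose conception cannot be dated clearly after dosing, replace the end-of-participation limit with remote follow-up by existing staff, with the participant's agreement, until pregnancy outcome and neonatal status are known. Record any AE or SAE. Keep scheduled follow-up as it is for conceptions clearly after the last dose.

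In the same edit, state that a pregnancy first recognised after dosing starts, even if conceived before day 0, takes the post-start steps, including the IRB report and the obstetrician advice. This part is a wording clarification only.

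Cost: one or two sentences, and possibly a consent line if the consent form does not already cover it. If a case occurs, it means occasional remote contact for roughly 6 to 9 months (182 to 260 days) and collection of some neonatal health information; the IRB may want to confirm how that sits with the exclusion of neonates in 5.3.1. Conception dating is imprecise: an assumed error of 3 to 14 days would bring in conceptions up to day 1 + 3 = 4 to 1 + 14 = 15, so some unexposed pregnancies would also be followed. If no case occurs, nothing is spent.
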